#### 6.5.2 Prohibited Medicines

Subjects must not have received chemotherapy, immunotherapy, biologic therapy, or any other anticancer therapy within 5 x their elimination half-life, but no longer than 15 days, before the first dose of IMP administration (6 weeks for nitrosoureas or mitomycin C). Thus, the washout period for prior anticancer therapy is defined as 5 x the elimination half-life of the relevant anticancer therapy, up to a maximum of 15 days.

These therapies are generally prohibited during the treatment period and the DLT follow-up period.

Subjects with functional neuroendocrine tumor who have progressed clinically or radiographically on octreotide or lanceotide may remain on octreotide or lanceotide for control of hormonal syndromes and still be allowed on study. Similarly, subjects under stable hormone therapy (having received hormone therapy for > 3 months) may remain on hormone therapy and are allowed in the study.

Radiotherapy (involving < 30% of bone marrow) to any other lesion is allowed at any time beyond PTD 7.

Medications or herbal supplements known to be potent inhibitors or inducers of CYP3A or P-gp, OATP or OCT or drugs mainly metabolized by CYP3A, with a narrow therapeutic index are prohibited (unless as otherwise agreed to by the Sponsor). Refer to Drug Development and Drug Interactions for a classification of in vivo inhibitors (see Appendix II).

If the administration of a prohibited concomitant drug becomes necessary during the treatment period, eg, due to AEs, the subject should be discontinued from the study treatment and complete all assessments listed under the Safety Follow-up (PTDs 15, 22, and 30) and End-of-Study visits.

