## 8.5.4.1 Adverse Events

Adverse events will be coded according to Medical Dictionary for Regulatory Activities. Severity of AEs will be graded using the NCI-CTCAE V4.03 toxicity grading scale.

The incidence of treatment-emergent AEs regardless of attribution and AEs defined as related to M3541 / RT will be summarized by Preferred Term and System Organ Class, and described in terms of intensity and relationship to M3541 / RT. Adverse events (serious and non-serious) will be considered TEAEs when emerging in the on-treatment period, defined as the time from the first IMP administration to the last administration date + 30 days (PTD 30) or the earliest date of subsequent anticancer drug therapy minus 1 day, whichever occurs first, unless otherwise stated. In addition, the AEs will be described for the period up to 1 year after the last dose of RT.

All premature terminations will be summarized by primary reason for treatment withdrawal.

All reported deaths during therapy and deaths within 60 days after the first dose and deaths within 30 days after the last dose of study treatment as well as reasons for death will be tabulated (for all subjects enrolled). Deaths within 1 year from last dose of RT and reasons for the death will also be tabulated.

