Presentation of pharmacokinetic/biomarker concentration data

Pharmacokinetic/biomarker concentration data will be descriptively summarized per dose level using: number of non-missing observations (N), arithmetic mean (Mean), SD, coefficient of variation (CV%), Min, median, and Max.

Descriptive statistics of PK/biomarker concentration data will be calculated using values with the same precision as the source data, and rounded for reporting purposes only. The following conventions will be applied when reporting descriptive statistics of PK/biomarker concentration data:

Mean, Min, Median, Max: 3 significant digits

SD: 4 significant digits

CV%: 1 decimal place

Presentation of pharmacokinetic parameter data

Pharmacokinetic parameter data will be descriptively summarized per dose level using: N, Mean, SD, CV%, Min, Median, Max, geometric mean (GeoMean), and the geometric coefficient of

variation (GeoCV) and the 95% CI for the GeoMean (lower CILCI 95% GeoMean, Upper CIGM, UCI 95% GeoMean).GM)

The following conventions will be applied when reporting descriptive statistics of PK parameter data:

Mean, Min, Median, Max, GeoMean, 95% CI: 3 significant digits

SD: 4 significant digits

CV%, GeoCV%: 1 decimal place

Definition of baseline:

The last non-missing measurement prior to first administration of M3541 will be used as the baseline measurement.

Definition of treatment day:

Treatment day 1 is defined as the date of first administration of M3541, the day before is defined as Treatment day –1 (no Treatment day 0 is defined).

Definition of fraction day:

Fraction days are defined as days of radiotherapy administration.

Definition of on-treatment period for safety analyses:

On-treatment period for safety analyses will be the time from the Treatment day 1 until the last M3541 administration date + 30 days (PTD 30), the earliest date of subsequent anticancer drug therapy minus 1 day or the clinical cut-off date (if the treatment is still ongoing), whichever occurs first.

Subsequent anticancer drug therapy date will be based on "Anti-cancer treatment after discontinuation", "Radiotherapy after discontinuation", and "Surgery after discontinuation" eCRF pages.

Definition of duration:

Duration will be calculated by the difference of start and stop date + 1 (e.g. survival time (days) = date of death – date of first dose + 1), if not otherwise specified.

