12.1 Prior Anti-Cancer Treatments and procedures

The prior anti-cancer treatments and procedures are collected under the "Prior anti-cancer drug therapies", "Prior anti-cancer surgeries", and "Prior anti-cancer radiotherapy" eCRF pages.

The following listings of prior anti-cancer treatments and procedures will be provided:

- Listing of prior anti-cancer drug therapies;
- Listing of prior surgeries;
- Listing of prior radiotherapy.

These will include the subject ID, dose level and all the relevant collected data fields on the corresponding eCRF pages.

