12.4 Concomitant Procedures

Concomitant procedures are procedures which are undertaken any time on-trial. These will be listed according to the CRF page "Concomitant Procedures".

In case the date values will not allow to unequivocally allocate a procedure to concomitant procedure, the approach described at section 9 will be followed.

The listing will include: dose level, subject ID and all corresponding collected data fields on the corresponding eCRF page.

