12.6 Anti-cancer, radiotherapy and surgery post-treatment

Anti-cancer, radiotherapy and surgery post-treatment will be listed according to "Anti-cancer treatment after discontinuation", "Radiotherapy after discontinuation" and "Surgery after discontinuation" eCRF pages. The 3 listings will include: subject ID, dose level and all corresponding collected data fields on the corresponding eCRF page.

13 Treatment Compliance and Exposure

Population: SAF Analysis Set

Treatment compliance and exposure will be listed and summarized by dose level and overall using SAF analysis set.

All dosing calculations and summaries will be based on "M3541 Administration" and "Radiotherapy Administration" eCRF pages.

Subjects should receive treatment with M3541 at a starting dose of 50 mg QD, which should be given 1 hour and 45 minutes (+/- 15 minutes) before each RT fraction (3 Gy) for up to 10 fractions. Based on nonclinical assumptions, the pre-planned dose levels are 50, 100, 200, 300, 500, and 800 mg; however, the number of dose levels and the actual dose to be explored in each subsequent cohort remains to be determined.

Number of days of therapy

The number of fraction days of Radiotherapy treatment and the number of days of M3541 therapy will be summarized by dose level.

Additionally, number and percentage of subjects in the following exposure categories will be reported by dose level:

- [1 day 4 days]
- [5 days 7 days]
- [8 days 9 days]
- 10 days
- > 10 days

Cumulative dose

The cumulative dose (mg) of M3541 will be calculated as the sum of the total daily doses that the subject received.

The cumulative dose (Gy) of RT will be calculated as the sum of the total daily doses that the subject received.

Compliance with treatment

The compliance with the treatment is defined as:

For M3541:

Relative dose intensity (%) =
$$\left(\frac{\text{cumulative dose (mg)}}{10 * \text{planned daily dose (mg)}} * 100\right)$$

• For RT:

Relative dose intensity (%) =
$$\left(\frac{\text{cumulative dose (y)}}{10 * \text{planned daily dose (y)}} * 100\right)$$

The compliance with the treatments will display using the following categories:

- > 100%
- 100%
- [80% 100%[%[
- [65% 80% [
- [50% 65% [
- < 50%

The following summary tables will be provided for M3541 and RT administrations by dose level:

- Number of fraction days for Radiotherapy and number of days of M3541 therapy
- Cumulative dose (mg for M3541 and Gy for RT) and relative dose intensity

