A swimmer plot displaying some key radiological milestones will be produced for each dose level separately. For each subject, the time from treatment start until end of treatment and end of follow-up (last date known to be alive or date of death) will be represented. In addition, the following information will be displayed: time to best overall confirmed response (CR, PR or SD), time to progression, time to the administration of first anticancer therapy and status at the end of the follow-up (alive or dead).

For subjects alive, the last known alive date will be used to determine the end of follow-up and it will be derived using the following dates:

- Last known alive date collected in the "Subject Status / Survival Follow-Up" eCRF page (SSSTDTC variable from SS SDTM domain to be used)
- · All patient assessment dates:
 - Laboratory assessments using information from "Serology", "Hematology", "Biochemistry", "Coagulation", "Urinalysis", "Microscopic analysis" and "Pregnancy test" eCRF pages (LBDTC variable from LB SDTM domain to be used)
 - Vital signs using information from "Vital signs" eCRF page (VSDTC variable from VS SDTM domain to be used)
 - Performance status using "ECOG Performance status" eCRF page (QSDTC variable from QS SDTM domain to be used)
 - ECG, using information from "Electrocardiogram" eCRF page (EGDTC variable from EG SDTM domain to be used)
 - Tumor assessments using "Tumor assessments" eCRF pages (TRDTC variable from TR SDTM domain to be used)
- Start and end dates of anti-cancer therapies administered after study treatment discontinuation using "Anti-cancer treatment after discontinuation", "Radiotherapy after discontinuation" and "Surgery after discontinuation" eCRF pages (CMSTDTC and CMENDTC variable from CM SDTM domain to be used)
- AE start and end dates using "Adverse events" eCRF page (AESTDTC and AEENDTC variables from AE SDTM domain to be used)
- Study treatment administration dates using "M3541 Administration" and "Radiotherapy Administration" eCRF pages (EXSTDTC variable from EX SDTM domain to be used)

A listing will provide the following information on PFS times: dose level, subject ID, date of first and last M3541 administration, date of event/censoring and relative day, event/censoring reason, time to event in months.

An additional listing on survival follow-up will contain all the fields from "Subject Status/Survival Follow-Up" and "Survival Follow-Up/Progression Disease" eCRF pages.

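### SAP section 9 ends the on-treatment period at anticancer drug therapy but dates that event from radiotherapy and surgery pages too, which can shorten the TEAE window without SAP section 7 saying so

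*SAP*

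**What the plan says.** Protocol 8.5.4.1 counts an adverse event as treatment-emergent if it emerges once IMP has been started and no later than "the last administration date + 30 days (PTD 30) or the earliest date of subsequent anticancer drug therapy minus 1 day, whichever occurs first". The same clause then leaves room for exceptions where these are stated.

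SAP section 9 repeats the rule for all safety analyses. The period opens with the first M3541 dose and lasts "until the last M3541 administration date + 30 days (PTD 30), the earliest date of subsequent anticancer drug therapy minus 1 day", with the clinical cut-off as a further limit if treatment is still ongoing. The next sentence gives the data source: "Subsequent anticancer drug therapy date will be based on 'Anti-cancer treatment after discontinuation', 'Radiotherapy after discontinuation', and 'Surgery after discontinuation' eCRF pages".

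SAP section 7 declares two departures from the protocol: the added pain summaries and the omitted intermittent schedules. It does not mention the on-treatment period.

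The window decides which events are TEAEs (SAP 15.2), and so what enters the AE frequency tables (SAP 15.2.1). It also limits the worst-grade laboratory shift tables (SAP 15.4).

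On radiotherapy after study treatment, Protocol 6.5.2 says: "Radiotherapy (involving < 30% of bone marrow) to any other lesion is allowed at any time beyond PTD 7".

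**The concern.** The definition names one kind of event and the derivation picks up three. A programmer who follows the second sentence builds a shorter window than the first sentence describes, and a reader of the tables would not know.

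The trigger is foreseeable. Subjects are enrolled because they need palliative RT, and the protocol allows RT to other lesions well inside the 30-day window. If such a course closes the window, later events and laboratory values drop out of the summary safety tables. The DLT evaluation period has its own end date, so the DLT table and the TEAE tables could disagree about the same event. With planned cohorts of 3, one subject missing from a TEAE row at a 3-subject dose level moves that row by 1/3, or 33 percentage points.

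**Working it through.** **Step 1. Is the word drug loose shorthand?** The SAP's own usage points both ways, but mostly to no.

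- SAP 12.1 keeps the three kinds of prior treatment apart: they "are collected under the 'Prior anti-cancer drug therapies', 'Prior anti-cancer surgeries', and 'Prior anti-cancer radiotherapy' eCRF pages".
- SAP 12.6 reports the three post-treatment pages separately: "The 3 listings will include: subject ID, dose level and all corresponding collected data fields on the corresponding eCRF page".
- SAP 14.2, for the last known alive date, groups the same three pages as "Start and end dates of anti-cancer therapies administered after study treatment discontinuation", without the word drug.
- SAP 14.2 also bases PFS on the three pages together and censors at new anti-cancer treatment, again without drug.

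Where the SAP means all three pages it elsewhere omits drug. Section 9 is the exception.

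**Step 2. Would permitted RT reach the radiotherapy page?** SAP 12.6 heads these pages as post-treatment, which makes it likely. No passage says so, and another page exists: "Concomitant procedures are procedures which are undertaken any time on-trial". The routing is therefore an assumption.

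**Step 3. Days lost.** Inputs: Monday start, 10 fractions without interruption, protocol v5.0 numbering (PTD 1 is the day after the last dose, Protocol Table 1), and DLT evaluation ending 14 days after the last M3541/RT (SAP section 9).

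- FD 10 falls on trial day 12, a Friday, so PTD p = trial day 12 + p.
- The full window ends on day 12 + 30 = day 42 = PTD 30. Protocol Figure 1 also places PTD 30 on trial day 42.
- Non-study RT starting on PTD p ends the window on PTD p - 1.
- Follow-up days lost = 30 - (p - 1) = 31 - p.
- DLT follow-up days outside the window = max(0, 14 - (p - 1)) = max(0, 15 - p).

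The first permitted day is PTD 8, trial day 20, a Saturday. If RT starts only on weekdays (assumption), the earliest start is Monday PTD 10.

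| RT starts | Window ends | Follow-up days lost (of 30) | DLT follow-up days outside (of 14) |
|---|---|---|---|
| PTD 8 (weekend start) | PTD 7 | 31 - 8 = 23 | 15 - 8 = 7 |
| PTD 10 | PTD 9 | 31 - 10 = 21 | 15 - 10 = 5 |
| PTD 14 | PTD 13 | 31 - 14 = 17 | 15 - 14 = 1 |
| PTD 17 | PTD 16 | 31 - 17 = 14 | 0 |
| PTD 24 | PTD 23 | 31 - 24 = 7 | 0 |

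**Step 4. Laboratory visits.** A visit held on PTD v is lost when v is at least p and no more than 30. Under Protocol Table 1, footnote c, the PTD 15 visit is held on Monday PTD 17, and the PTD 22 visit on PTD 20, 21 or 24. PTD 30 is a Sunday: a visit on Friday PTD 28 would be lost, while one postponed to Monday PTD 31 lies outside the window anyway. A PTD 10 start therefore costs 2 or 3 laboratory visits.

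**Step 5. Consequence.** A DLT starting on PTD 10 to 14 in that subject is inside the DLT evaluation period and counts in the SAP 15.1.1 table. It is outside the on-treatment period and so in none of the SAP 15.2.1 frequency tables.

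**The case against.** The strongest reply is that the SAP may set this rule. Protocol 8.5.4.1 allows stated exceptions, Protocol 8.5 leaves full analysis details to the SAP, and section 9 names its pages plainly enough to yield one date. SAP 14.2 treats the same three pages together for PFS. Ending the window at a new RT course is also defensible, because RT is a trial treatment here and another course confounds attribution. On this view drug is a leftover word.

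This stands in part. A reader might infer that the SAP breaches the protocol; the allowance for exceptions means the documents do not support that. It does not remove the contradiction inside section 9 or explain the silence of section 7.

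A reader might also infer that events vanish from the report or that the primary endpoint is compromised. Neither follows. All AEs are listed whether treatment-emergent or not, and related AEs are listed outside the window too. The laboratory listings, the grade 3 or higher listing and the laboratory spider plots are not cut. The death tables, the DLT table and safety committee review do not depend on this window.

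Nor should the narrowness of the shift tables be blamed on the RT page. Protocol 8.5.4.2 summarizes worst on-study grades after the first IMP administration, so SAP 15.4 is narrower simply by using the on-treatment window.

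Finally, the harm needs a chain: non-study RT inside the window, entry on that page, and a later event or worst value. No document gives a frequency. For surgery the effect is smaller, since Protocol 6.5.3 bars major surgery during the study.

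**Conclusion.** The point holds as an internal contradiction in SAP section 9, undeclared in section 7, that can change summary safety results. A wider cut is permissible, but it must be labelled as such.

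For a v5.0 subject treated on time from a Monday, weekday RT on PTD 10 would cost 21 of 30 follow-up days, 5 of 14 DLT follow-up days and 2 or 3 laboratory visits; later starts cost less. This rests on the RT being recorded on the radiotherapy after-discontinuation page. Subjects enrolled under earlier versions have different PTD numbering and a DLT period ending 23 days after the last dose, so these counts do not carry over to them.

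The effect is confined to the TEAE and laboratory shift tables. The number of subjects affected is unknown and may be zero. It should be fixed before the tables are produced.

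**What to change.** Reconcile SAP section 9 with Protocol 8.5.4.1: date subsequent anticancer drug therapy from the 'Anti-cancer treatment after discontinuation' page only. In the TEAE and shift outputs, flag events and worst laboratory values that start after non-study RT or surgery, and give the count of flagged subjects.

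If the sponsor does intend RT and surgery to end the period, delete the word drug, declare the change in SAP section 7, and report how many subjects and events through PTD 30 the cut removes. Either way, one line saying which eCRF page takes RT permitted under Protocol 6.5.2 would settle the routing question.

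The cost of the first route is one sentence, one derived date and one flag on data already collected. Its downside is that some events confounded by later local therapy enter the TEAE counts; the flag identifies them. This fix does not by itself restore the Protocol 8.5.4.2 rule for laboratory grades.

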# Planned study and treatment duration per subject:

The study period per subject includes an up to 21-day screening period, a scheduled 2-week treatment period, followed by a 2-week DLT follow-up period and follow-up for up to 1 year after RT has been completed (note, after the 1-year follow-up, the Investigator will contact the subject every 3 months [ $\pm$  1 month, telephone contact is acceptable] until the defined end of the study to enquire and monitor for late appearing RT-related toxicity).

Up to a 3-FD delay during the treatment period will be allowed in the once per FD dosing schedule, which may extend the total treatment period of 2 weeks. The thrice weekly schedule will not allow to delay M3541 dosing (if not treated (due to toxicity or other reasons) on the scheduled timing, no treatment will be given). The twice weekly schedule will allow a 24-hour treatment delay (if not treated on the scheduled day for toxicity or other reasons, as long as treatment-enabling conditions are reached the next radiotherapy day, the subject can be dosed that day).

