AE = adverse event; β-HCG = beta-human chorionic gonadotropin; BPI-SF = Brief Pain Inventory – Short Form; CT = computed tomography; ctDNA = circulating tumor DNA; DLT = dose-limiting toxicity; ECG = electrocardiogram; ECOG PS = Eastern Cooperative Oncology Group performance status; eCRF = electronic case report form; EoS = End-of-Study; FD = Fraction Day (days when RT and M3541 are given); FU = follow-up; Gy = Gray; HBV = hepatitis B virus; HCV = hepatitis C virus; HIV = human immunodeficiency virus; MRI = magnetic resonance imaging; PK = pharmacokinetics; PTD = Post-treatment Day (starting the day after the last dose of RT and M3541 until 1 year later); QTCF = Fridericia corrected QT interval; RECIST 1.1 = Response Evaluation Criteria in Solid Tumors version 1.1; RT = radiotherapy; TEAE = treatment-emergent adverse event.

Note: Where scheduled post-treatment visits coincide with a weekend or holiday, they may be postponed to the next working day (up to + 2 days). The relevance of any safety finding during this additional time in the context of a DLT or any other late toxicity will be reviewed by the Safety Monitoring Committee.

- a. All subjects will be followed up for disease progression until 1 year after RT is completed, or earlier due to any reason whereby tumor assessments are no longer applicable (eg, PD, if a new treatment is started, withdrawal of consent). The reason for early discontinuation should be captured in the source document. If EoS occurs prior to PTD 365, all assessments must be done as planned for PTD 365. All subjects will be followed for survival and for delayed AEs for up to 1 year (and beyond for AEs) from PTD1. After the 1 year follow-up, the Investigator will be asked to contact subjects every 3 months (± 1 month, phone call is acceptable) until the defined end of the study (see Section 5.7) to enquire and monitor for late appearing RT-related toxicity.

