- b. FD 1 is the first dose of M3541 and first fraction of RT. Planning of the RT will follow institutional guidelines and will start on a Monday (with the first Saturday and Sunday as a M3541 / RT holiday). In cohorts where required, subjects will be asked to stay overnight in a supervised environment on FD 1 unless the PK sampling and ECG assessment at 8 and 12 hours postdose can be completed otherwise. FD 10 is the last administration of M3541 / RT and the DLT follow-up period will start on the following day (PTD 1). In case of premature withdrawal from the study during the treatment period, the assessments scheduled for the visit on FD 10 should be performed. In such cases, this visit will be considered the EoS visit. If FD 10 is on a Friday then safety laboratory assessments and urinalysis (as required) must be done on FD 9.

- c. The 2-week DLT follow-up period (PTDs 1 through 14) starts on the day after the last administration of M3541 / RT. With the treatment period starting on a Monday, PTD 15 will land on a Saturday. The PTD 15 visit has a + 2 days visit window, thus subjects should present to the clinic on the following Monday for the PTD 15 DLT follow-up visit. PTD 22 will also land on a Saturday. The PTD 22 visit has a ± 2 days visit window, thus subjects should present to the clinic for this safety assessment on either the preceding Thursday/Friday (PTDs 20/21) or the following Monday (PTD 24). Subjects with ongoing AEs should present to the clinic throughout the DLT follow-up period as appropriate and instructed by the Investigator. See Section 6.5 and subsections for allowed and prohibited medications during the DLT period.
- d. Subjects must meet all inclusion criteria and not any exclusion criteria prior to enrollment. Hepatitis B and C results obtained within 3 months prior to screening are still valid for the purpose of this study. In the case of new clinical laboratory abnormalities detected prior to the first dose, the eligibility of the subject should be reconsidered.

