# 7.1.3 Dose-limiting Toxicity Evaluation Period

The DLT evaluation period will be 4 weeks in duration, including the 2-week treatment period (including a 2-day M3541 / RT holiday after FD 5) plus a 2-week DLT follow-up period that starts on the day after the last administration of M3541 / RT (see Figure 1). After the M3541 / RT treatment period, subjects will return to the clinic on PTD 15 (+ 2 days) for assessments (including the BPI-SF as applicable) as outlined in Table 1. The DLT evaluation period could exceed the 4-week period only if M3541 / RT has been interrupted and given over a period exceeding 2 weeks.

Subjects with ongoing AEs should present to the clinic throughout the DLT follow-up period as appropriate and instructed by the Investigator (see Section 6.5 and subsections for allowed and

prohibited medications). It is expected that the Investigator will follow his / her subjects and will ask subjects to come in to the clinic (and document) when AEs are known to happen. In absence of any new or major toxicity / AE during the DLT follow-up period, the subject need only be seen on PTD 15 (+ 2 days) and PTD 22 ( $\pm$  2 days).

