The time since an event (e.g. time since first diagnosis) will be calculated as reference date minus date of event.

Definition of DLT evaluation period:

For all subjects enrolled before protocol v5.0 (amendment 4.0):

The DLT evaluation period will start on the day of the first administration of M3541 / RT and will end 23 days after the last administration of M3541 / RT (2-day M3541 / RT holiday after the last fraction day (FD) plus a 3-week DLT follow-up period that starts on the third day after the last administration of M3541 / RT). The end date of the period will be calculated as follows:

Date of last administration of M3541/RT + 23 days

The DLT evaluation period will be 5 weeks in duration, unless M3541 / RT has been interrupted for up to 3 days.

For all subjects enrolled under or after protocol v5.0 (amendment 4.0):

The DLT evaluation period will start on the day of the first administration of M3541 / RT and will end 14 days after the last administration of M3541 / RT (2-week radiotherapy treatment period plus a 2-week DLT follow-up period that starts on the day after the last administration of M3541 / RT). The end date of the period will be calculated as follows:

Date of last administration of M3541/RT + 14 days

The DLT evaluation period will be 4 weeks in duration, unless M3541 / RT has been interrupted and given over a period exceeding 2 weeks.

Definition of analysis time points

Actual time elapsed from first M3541 administration in hours will be derived as:

$$Actual\ time\ (hours) = \frac{Datetime\ of\ interest - Datetime\ first\ M3541\ dose}{3600}$$

Nominal time elapsed from first M3541 administration in hours will be derived according to the following rules:

- For results collected at screening, Nominal time = -1
- For results collected from fraction day 1 to fraction day 5:

Nominal time Nominal time =
$$(X - 1) * 24 + Y$$

• For results collected from fraction day 6 to fraction day 10:

Nominal time Nominal time =
$$(X + 1) * 24 + Y$$

With X = fraction day and Y = number of hours elapsed from M3541 administration on X. Y = 0 for predose samples.

Of note, the nominal time will not be derived for unscheduled samples.

The time points at which assessments are expected are reported below (distinguishing among subjects enrolled before protocol v5.0 (EARLY) and under it (LATE)):

Table 4: Nominal time points for ECG, pharmacodynamics and immune system sampling

X	Y	Nominal Time from first M3541 dose (in hours)	ECG		ECG		ECG PD		IM	

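### Under protocol v5.0 the DLT window closes on PTD 14, before the closing DLT visit on PTD 15 to 17; read literally, the SAP leaves a DLT first dated at that visit out of the primary table

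*SAP*

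**What the plan says.** SAP section 9 states that, for subjects under v5.0, the period "will end 14 days after the last administration of M3541 / RT". Protocol Table 1, footnote c, has the same window: "The 2-week DLT follow-up period (PTDs 1 through 14) starts on the day after the last administration of M3541 / RT". Both documents call the whole period 4 weeks.

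The same footnote places the closing visit after it: "thus subjects should present to the clinic on the following Monday for the PTD 15 DLT follow-up visit". Protocol 7.1.3 adds that, when there is no new or major toxicity, "during the DLT follow-up period, the subject need only be seen on PTD 15 (+ 2 days) and PTD 22". On laboratory timing, footnote b says: "If FD 10 is on a Friday then safety laboratory assessments and urinalysis (as required) must be done on FD 9". On delays, the synopsis says: "Up to a 3-FD delay during the treatment period will be allowed in the once per FD dosing schedule".

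The protocol foresees late findings. The note under Table 1 says "Where scheduled post-treatment visits coincide with a weekend or holiday, they may be postponed to the next working day", and it gives the SMC the task of reviewing "The relevance of any safety finding during this additional time in the context of a DLT".

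On counting, SAP 15.1 defines the primary endpoint as a DLT within the section 9 period. SAP 15.1.1 takes DLTs from either the investigator flag or the SMC-review flag, and limits the summary table to the DLT period. SAP 8.2 admits a subject without a DLT to the DLT set if at least 80% of each treatment was given and a safety result exists on or after the period's end date. Protocol 8.4 asks for a safety assessment on PTD 15 (+2 days).

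**The concern.** DLT occurrence is the primary endpoint. The visit that closes DLT follow-up, and that shows a subject has completed it, lies outside the dates within which a DLT can count. The same visit can therefore make a subject evaluable without a DLT while a DLT first dated there is excluded. The error runs in one direction only: it can lower the DLT count and never raise it. The documents also pull against each other, because the protocol asks the SMC to judge such findings and the SAP accepts the SMC's flag, yet the SAP's date limit makes no exception for it.

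**Working it through.** **Inputs.** FD 1 on a Monday (day 1), five fraction days per week and a visit at PTD 15 +2 days (protocol Table 1, footnotes b and c); window end = last administration + 14 days (SAP 9); delay of up to 3 FDs (synopsis).

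**Step 1: the plan's own figure.** With no delay, FD 10 is Friday, day 12. Window end = 12 + 14 = day 26, a Friday, PTD 14. This reproduces the PTD 1 to 14 window. The stated 4 weeks is nominal: 28 days would end on PTD 28 − 12 = 16, still short of the Monday visit. The rule for subjects enrolled before v5.0 gives 12 + 23 = 35 days, exactly 5 weeks.

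**Step 2: window against visit.** The visit runs from last administration + 15 to + 17 and the window ends at + 14, so they never overlap.

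| FDs lost | FD 10 | Window ends | PTD 15 | Usual visit | Last on-treatment labs | Lab gap |
|---|---|---|---|---|---|---|
| 0 | Fri, day 12 | day 26 | Sat, day 27 | Mon, day 29 (PTD 17) | FD 9, day 11 | 29 − 11 = 18 days |
| 1 | Mon, day 15 | day 29 | Tue, day 30 | day 30 | FD 10, day 15 | 15 days |
| 2 | Tue, day 16 | day 30 | Wed, day 31 | day 31 | FD 10, day 16 | 15 days |
| 3 | Wed, day 17 | day 31 | Thu, day 32 | day 32 | FD 10, day 17 | 15 days |

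The Table 1 note covers the first row, where the visit moves off a weekend. It does not cover the other three, where PTD 15 is a weekday unless it happens to be a holiday.

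**Step 3: scheduled safety labs inside PTD 1 to 14.** None. The 240-hour ECG and PK contact falls inside but has no safety labs. That labs are drawn at PTD 15 is legible only in the amendment copy of Table 1 (Appendix V), because those rows of the current table are broken in the extracted text.

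**Step 4: follow one DLT dated at the closing visit through the SAP, read literally.**
- At least 80% of each treatment received: the visit meets the completion criterion in 8.2, so the subject is in the DLT set. The event is later than the section 9 end date, so 15.1.1 counts the subject under no DLT.
- Below 80%: without a DLT inside the window neither criterion in 8.2 is met. The subject leaves the DLT set and is replaced under protocol 5.5.2.

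**Step 5: size of one uncounted event.** Exact (Clopper-Pearson) 95% limits: lower = Beta(0.025; x, n − x + 1), upper = Beta(0.975; x + 1, n − x). For x = 0 the upper limit is 1 − 0.025^(1/n).
- Three subjects: 1/3 (0.8% to 90.6%) becomes 0/3 (0% to 70.8%).
- Six subjects, the number the synopsis gives for validating a dose: 1/6 (0.4% to 64.1%) becomes 0/6 (0% to 45.9%).

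The SAP plans counts only, so these intervals just show scale. They say nothing about how likely such an event is.

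**The case against.** The best defence is that the SAP follows the protocol. Both end the window on PTD 14, protocol 5.1.1 limits DLTs to events in the evaluation period, and a visit just after a fixed window is an ordinary completion check at which earlier onset dates can be recorded. This stands: the gap starts in the protocol, and a reader who infers that the SAP departed from it would be wrong.

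Second, exclusion is one reading. SAP 15.1.1 identifies DLTs by flag, gives no date-filter algorithm, and does not say which date of a laboratory event is tested. Table 1 prints the PTD 15 visit in the DLT follow-up column. A programmer might count the event. This also stands, and it is why the point is put as a literal reading. An ambiguity in the primary endpoint still has to be settled in writing.

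Third, the scope is small. Symptomatic events and subjects with ongoing AEs are seen earlier. Criteria lasting more than 3 or 5 days need repeat samples. Laboratory abnormalities are reported as AEs only under the conditions in protocol 7.4.1.1. At Amendment 4.0 no DLT had been seen in 8 subjects. All of this is accepted.

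A reader might further infer that dose decisions or the MTD would be wrong. The documents do not support that. The reference dose d_ref and SAP Addendum 1 are not available, the model does not bind the SMC, and the SMC sees all safety data. Nor is the event lost: the primary-analysis cut-off is PTD 30, and the all-AE listing shows the DLT flag and its source. The TEAE tables are a weaker safeguard, because their period ends the day before any subsequent anticancer therapy.

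**Conclusion.** The point holds in a narrow form. For v5.0 subjects, protocol and SAP alike close the DLT window before the protocol's own closing DLT visit, in every delay pattern allowed. Read literally, a DLT first dated on PTD 15 to 17 is missing from the primary table even if the SMC confirms it. A subject with at least 80% of each treatment is then counted as having no DLT; a subject below 80% drops out of the DLT set.

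The events at risk are new, silent laboratory findings that a single sample can establish, such as Hy's law or unexplained Grade 4 anemia. One of them moves 1/3 to 0/3, or 1/6 to 0/6. No effect on escalation or the MTD is shown. The conclusion assumes a Monday start, safety labs at PTD 15 as in the amendment copy of Table 1, and that the section 9 dates are applied to the sample date. It should be fixed because the rule can only undercount the primary endpoint and the correction is nearly free.

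**What to change.** Leave the protocol's 2-week follow-up unchanged. Moving the whole period to PTD 17 might look simpler, but the limits on other anticancer therapy (protocol 6.5.2) and on joining another study (protocol 5.5.2) are tied to it, and Amendment 4.0 shortened it so that subjects could reach their next treatment sooner. Change the counting rule instead:

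- **SAP 15.1.1 and 8.2:** state that a DLT flagged by the investigator or the SMC and first found at the PTD 15 (+2 days) visit, up to PTD 17, counts in the primary table and for DLT-set membership. Say which date is tested. Flag any such event that follows the start of subsequent anticancer therapy.
- **SAP Table 2:** state that the SMC cut-off for the last subject of a cohort is the date of that visit. This matters because SAP 9 keeps data after the cut-off out of listings and summaries.
- **Protocol:** reconcile the PTD 1 to 14 window, the period limit in the DLT definition, the closing visit and the Table 1 SMC note with this rule, including visits that fall on a weekday.

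The cost is wording and one date derivation, with no added visits, samples or subjects. The drawbacks are that the counting window varies by up to 3 days between subjects (PTD 14 to 17) and that the DLT count may be slightly less favourable.
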